#### 9.2.2 Secondary Efficacy Endpoints

Further efficacy of DZD will be evaluated by assessment of:

- Proportion of patients who suffer relapse, defined as recurrent disease caused by a strain identical to the baseline isolate, within 12 months post randomisation, out of patients completing 16 weeks of therapy and achieving stable culture conversion to negative (SCC) as defined below by week 08, with no positives to follow by the week 16 visit.
- Time to recurrent TB, and to relapse, within 12 months post randomisation
- Time to stable sputum culture conversion (SCC) to negative on liquid media (defined as two negative cultures without an intervening positive culture). Time will be measured as time on treatment until the first negative culture.
- Proportion of participants who achieved SCC at each time point during treatment
- Proportion of participants with negative sputum culture on solid media at WK 08 and other timepoints
- Proportion of participants developing drug resistance among those not converting to negative culture

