5.2.2. Secondary Efficacy Endpoints

- Proportion of participants who suffer relapse, defined as recurrent disease caused by a strain indistinguishable to the baseline isolate (using whole genome sequencing), within 12 months post randomization, out of participants completing 16 weeks of therapy and achieving sustained sputum culture conversion defined as two successive negative liquid media cultures at or before WK08, with no positives to follow by the week 16 visit. Full definition of relapse in section 11.2.
- Time to recurrent TB, and to relapse, within 12 months post randomization.
- Time to culture conversion to negative on liquid media (defined as two negative cultures without an intervening positive culture).
- Proportion of participants converting to negative sputum culture in liquid media (defined as two negative cultures
 without an intervening positive culture) at each time point during treatment.
- Proportion of participants with negative sputum culture on solid media at WK 08 and other time-points.
- Proportion of participants developing drug resistance among those not converting to negative culture.

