11.2. Relapse

An important secondary outcome is the proportion of participants who suffer relapse among those completing 16 weeks of therapy, achieve early culture conversion to negative in liquid media if there is a culture negative timepoint at two consecutive visits, the first of which is at or before week 08, without an intervening culture positive timepoint, and terminating therapy.

All participants will be classified as follows:

- Not achieved culture conversion to negative before or at week 8 after randomization (based on the analysis visit window).
 These participants will not end treatment at week 16 according to the protocol and therefore are not included in the relapse analysis.
- Relapse defined as having two consecutive culture positive timepoints without an intervening culture negative timepoint where the first occurs after Week 16 after randomization (based on the analysis visit window) and the recurrence strain of MTb is shown to be the same as that at baseline. If strain typing results are missing or inconclusive, a recurrence will be considered a relapse (rather than a reinfection).
- Reinfection defined as having two consecutive culture positive timepoints without an intervening culture negative timepoint where the first occurs after Week 16 after randomization (based on the analysis visit window) and the recurrence strain of MTb is shown to be different from that at baseline.
- Died at any point during the study
- Culture positive timepoint when last seen (not meeting criteria for other outcomes above)
- Culture negative timepoint when last seen (not meeting criteria for other outcomes above)

Outcomes will be tabulated by treatment arm among all in the ITT analysis population and among those in the AA analysis population.

A sensitivity analysis will be conducted repeating this relapse analysis using the second definition of time to culture conversion described below under the latter part of section 11.4.

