11.3. Time to recurrent TB and relapse

Time to recurrent TB will be defined as time from randomization to first culture positive timepoint that leads to a classification of relapse or reinfection. Participants without reinfection or relapse will be censored at time of last culture result. Time to relapse will be defined in the same way, except considering only relapses (and not reinfections) as events.

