% With culture conversion at 8 weeks	xx.x%	xx.x%	xx.x%	xx.x%	xx.x%
% With culture conversion at 12 weeks	xx.x%	xx.x%	xx.x%	xx.x%	xx.x%

% With culture conversion at 14 weeks	xx.x%	xx.x%	xx.x%	xx.x%	xx.x%
% With culture conversion at 16 weeks	xx.x%	xx.x%	xx.x%	xx.x%	xx.x%
Hazard Ratio (95% CI)	xx (xx, xx)				

 $Figure\ 2.1:\ Kaplan-Meier\ plot\ of\ time\ to\ first\ of\ two\ negative\ culture\ conversions.$

{including Kaplan - Meier plot comparing 4 arms with number at risk/control below}

Table 2.10 Summary of Relapse by Treatment Arm

Total in ITT analysis population	Arm 1 D0 (N=x) n (%)	Arm 2 D400 (N=x) n (%)	Arm 3 D800-OD (N=x) n (%)	Arm 4 D1200 (N=x) n (%)	Arm 5 D800-BD (N=x) n (%)	Total (N=x) n (%)
Not achieved time to stable culture conversion	xx (xx.x %)	xx (xx.x %)	xx (xx.x %)	xx (xx.x %)	xx (xx.x %)	xx (xx.x %)
Relapse	xx (xx.x %)	xx (xx.x %)	xx (xx.x %)	xx (xx.x %)	xx (xx.x %)	xx (xx.x %)
Time to relapse (mean +- SD)	xx (xx)	xx (xx)	xx (xx)	xx (xx)	xx (xx)	xx (xx)
Reinfection	xx (xx.x %)	xx (xx.x %)	xx (xx.x %)	xx (xx.x %)	xx (xx.x %)	xx (xx.x %)
Time to Reinfection (mean +- SD)	xx (xx)	xx (xx)	xx (xx)	xx (xx)	xx (xx)	xx (xx)
Death	xx (xx.x %)	xx (xx.x %)	xx (xx.x %)	xx (xx.x %)	xx (xx.x %)	xx (xx.x %)
Culture positive when last seen	xx (xx.x %)	xx (xx.x %)	xx (xx.x %)	xx (xx.x %)	xx (xx.x %)	xx (xx.x %)
Culture negative when last seen	xx (xx.x %)	xx (xx.x %)	xx (xx.x %)	xx (xx.x %)	xx (xx.x %)	(xx.x %)

Table 2.11 Summary of Drug resistance by Treatment and Visit:

Arm 1 D0 (N=x)	Arm 2 D400 (N=x)	Arm 3 D800-OD (N=x)	Arm 4 D1200 (N=x)	Arm 5 D800-BD (N=x)	Total (N=x)
----------------------	------------------------	---------------------------	-------------------------	---------------------------	----------------

Number of			
Participants			
Drug Name			
of			
Resistance			
Proportion			
of			
Participants			
developing			
drug			
resistance			
among those			
not			
converting			
to negative			
culture.			

Listing 2.1 Listing of all Drug Resistance

{This section will list a record of all drug resistance, including drug name, visit number, participant ID etc. F}

{Additional sensitivity analysis will be performed with alternative definitions of time to culture conversion, tables 2.8 and 2.9 will be repeated for each sensitivity definition of time to culture conversion.}

3. Safety Evaluation

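### The SAP defines relapse among early converters who completed 16 weeks, but tabulates it over the whole ITT population, so no planned output reports the endpoint as defined

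*SAP*

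**What the plan says.** Three places give a conditional denominator. Protocol 9.2.2 counts relapses "out of patients completing 16 weeks of therapy and achieving stable culture conversion to negative (SCC) as defined below by week 08", with no positives afterwards up to the week 16 visit. SAP 5.2.2 counts them "out of participants completing 16 weeks of therapy and achieving sustained sputum culture conversion". SAP 11.2 opens with "An important secondary outcome is the proportion of participants who suffer relapse among those completing 16 weeks of therapy", and adds that they converted early and ended therapy. Of those who did not convert by week 8, SAP 11.2 says: "These participants will not end treatment at week 16 according to the protocol and therefore are not included in the relapse analysis".

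SAP 11.2 then sorts all participants into six outcome classes, with non-conversion as the first and relapse as the second, and closes with: "Outcomes will be tabulated by treatment arm among all in the ITT analysis population and among those in the AA analysis population". Table 2.10 in the SAP appendix carries this out. Its stub reads "Total in ITT analysis population", each arm has a single N with n (%), and the first row is "Not achieved time to stable culture conversion", followed by the relapse row. No row gives the number eligible for the relapse endpoint, and there is no conditional percentage and no confidence interval. SAP section 6 makes ITT the primary population for every analysis except safety.

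**The concern.** A programmer who follows the tabulation sentence, the ITT default and the shell will divide relapses by the ITT total of the arm. That total includes non-converters, who have their own row and so cannot be counted as relapses. Under the protocol they are referred for standard treatment after week 16 instead of stopping.

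The resulting figure mixes two things: how many participants reached the point of stopping, and how many of those relapsed. Early conversion is an outcome that delpazolid dose is meant to influence, so the number eligible can be expected to differ between arms. An arm with few converters would then show a low relapse percentage partly because few of its participants could be counted as relapsing. The SAP calls this an important secondary outcome, and the trial's aim is to choose a dose.

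**Working it through.** The documents state no relapse rate, power or sample size for relapse, so there is no planned figure to reproduce. The check is on the algebra of the two denominators.

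**Inputs.** Arm size 15 (SAP 4.3). The number of converters and the relapse risk among them are not given. I assume 6 to 15 converters of 15, and a risk of 10% or 25%.

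**Identity.** Let N be the ITT total of an arm, c the number outside the non-converter row, and x the relapses. Then x/N = (c/N) × (x/c). The tabulated percentage equals the relapse proportion among converters only if everyone converts.

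**Equal risk, different conversion** (c/15 × risk):

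| Converters of 15 | True risk 25%: table shows | True risk 10%: table shows |
|---|---|---|
| 15 | 25.0% | 10.0% |
| 12 | 20.0% | 8.0% |
| 9 | 15.0% | 6.0% |
| 6 | 10.0% | 4.0% |

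**Ranking can reverse** (assumed counts, exact Clopper-Pearson 95% CIs):

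- One arm: 3 relapses among 14 converters. Conditional 3/14 = 21.4% (4.7 to 50.8); tabulated 3/15 = 20.0% (4.3 to 48.1).
- Another arm: 2 relapses among 7 converters. Conditional 2/7 = 28.6% (3.7 to 71.0); tabulated 2/15 = 13.3% (1.7 to 40.5).

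The second arm is worse among converters and looks better in the table.

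**Can a reader recover the endpoint from Table 2.10?** Only approximately. N minus the non-converter row is not the number who completed, qualified and stopped, for two reasons:

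- There is no row for non-completers. Someone who converted early and then discontinued before week 16 stays in the remainder.
- The primary conversion definition in SAP 11.4 disregards positive timepoints after conversion. Protocol 12.4 requires that none follow up to week 16 before therapy ends. Someone who converted and then had a positive at, say, week 10 counts as a converter in the table but did not qualify to stop. The second sensitivity definition in SAP 11.4 adds this condition, but SAP 11.2 applies it by repeating the same analysis, with the same layout.

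**The case against.** The strongest reply is that the SAP does not replace the conditional denominator. It states that denominator twice, the protocol states it too, and SAP 11.2 excludes non-converters from the relapse analysis. The tabulation sentence concerns the six-class breakdown of all participants, and no text or footnote says what the percentages are taken over. The appendix also describes the shells as guidance that may be updated. This stands as far as it goes: the fault is a contradiction within the plan, not a decision to analyse a different endpoint. It does not remove the fault, because the only relapse output specified still gives a figure that differs from the definition.

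A second reply is that nothing is concealed, since non-converters appear by arm beside the relapses. That also has force. A reader might infer that the table would mislead outright; in fact the imbalance is visible, and what is missing is the exact eligible number.

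A third is that relapse is descriptive. No test, model or decision rule uses it, and the primary efficacy analysis is the TTP exposure-response model. With at most 15 per arm, the intervals above overlap almost entirely on either base. This stands and limits the consequence.

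A reader might also infer that SAP 11.3 is wrong because "Participants without reinfection or relapse will be censored at time of last culture result", so that non-converters add event-free time. The documents do not support that. Both define time to recurrent TB and to relapse within 12 months of randomisation, without restriction to converters. The SAP describes no Kaplan-Meier or Cox analysis of relapse; Table 2.10 plans only a mean and SD of the times.

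**Conclusion.** The plan contradicts itself on the relapse denominator. As written, no planned output reports relapse among those who completed 16 weeks, converted early and stopped. The direction of the distortion is certain from the identity: at equal risk among converters, fewer converters gives a lower tabulated percentage. Its size is not known. At an assumed 25% risk, the shortfall runs from 0 points with 15 converters to 15 points with 6; at 10% it runs from 0 to 6 points. The reversal shown is a possibility under assumed counts, not a prediction.

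It would go too far to say that the all-ITT table is illegitimate or that the dose choice would be overturned. The table is a sound account of what happened to every treated participant, and at this sample size neither denominator would carry a dose conclusion on relapse alone. The inconsistency should still be settled before the final database lock, so that the percentage base is not chosen once the results are known.

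**What to change.** In SAP 11.2, state the denominator of the relapse proportion: participants who completed 16 weeks, met the protocol's full stop rule (including no later positive up to week 16) and stopped therapy. In Table 2.10, add that number for each arm, and report relapses among those participants over it with an exact 95% CI. Label the existing ITT and AA breakdown as an outcome or disposition table, and say that its percentages are of the column N. SAP 11.3 needs no change on this account.

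Optionally, add the proportion of all ITT participants who stopped at week 16 and were relapse-free to WK52. This keeps the randomised comparison, but the documents do not require it.

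The cost is a few lines of SAP text and a revision to one table shell. The reported relapse percentages will generally be higher and their intervals wider, as with 2/7 against 2/15 in the working.

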11.3. Time to recurrent TB and relapse

Time to recurrent TB will be defined as time from randomization to first culture positive timepoint that leads to a classification of relapse or reinfection. Participants without reinfection or relapse will be censored at time of last culture result. Time to relapse will be defined in the same way, except considering only relapses (and not reinfections) as events.

11.4. Time to culture conversion to negative on liquid media

Participants will be classified as having culture conversion to negative in liquid media if there are two consecutive culture negative timepoints without an intervening culture positive timepoint. Any other results will be ignored for the calculation of time to culture conversion. Culture timepoints will be classified as negative or positive according to the trial definition under 11.1.

Time will be taken from the date of randomization to the first occurrence of two consecutive negative culture timepoints.

Culture positive timepoints that occur after culture conversion has been achieved do not affect time to culture conversion.

This will be the primary definition of time to culture conversion. Primary analysis will be performed based on the primary definition. We will, in addition, perform two sensitivity analyses with alternative definitions of time to culture conversion:

- 1) The definition will be as above, with the exception that culture conversion can only be achieved if the two consecutive visits assessed as culture negative timepoints without an intervening culture positive timepoint are at least 28 days apart.
- 2) The definition will be as above, with the exception that culture conversion is only achieved provided no further culture positive timepoints occur after 'culture conversion', in the period up to and including the week 16 visits (a subsequent culture positive timepoint effectively 'cancels' out culture conversion).

12. Analysis Method

12.1. Analysis of time to culture conversion by dose group.

Descriptive summary statistics, such as mean/median of the time to culture conversion will be tabulated. Proportion of participants achieving culture conversion at each time point during treatment will be summarized using the Kaplan-Meier estimator with 95% confidence intervals.

A Cox regression model will be used to compare each arm with different DZD doses to the background regimen without DZD, in time to culture conversion. The analysis will be adjusted for the baseline cultures using time to positivity (TTP) at the time of screening and enrolment. Demographic and clinical characters, such as gender, age, race, BMI, HIV status, smoking, alcohol usage, will also be adjusted in sensitivity analyses. To check the Proportional Hazard (PH) assumption, we will do statistical tests and graphical diagnostics based on the Schoenfeld residuals. ¹² If the PH assumption is violated, cox regression models will be presented but interpretation will take into account this violation and alternative methods will be added including restricted mean survival time ¹³.

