#### **10.3** Inclusion Criteria

Participants are required to meet **all** the following criteria in order to be randomized:

- 1. Provide written, informed consent prior to all trial-related procedures including HIV testing.
- 2. Male or female, aged between 18 and 65 years, inclusive.
- 3. Body weight (in light clothing and with no shoes) between 40 and 90 kg, inclusive.
- 4. Newly diagnosed, previously untreated, drug susceptible pulmonary TB: presence of MTB complex and rapid molecular tests result confirming susceptibility to RIF and INH such as GeneXpert and/or HAIN MTBDR *plus*.
- 5. A chest X-ray (no older than 2 weeks) which, in the opinion of the Investigator, is consistent with TB.
- 6. Sputum positive on microscopy from concentrated sputum for acid-fast bacilli on at least one sputum sample (at least 1+ on the IUATLD/WHO scale).
- 7. The participant is willing to forgo consumption of foods high in tyramine for the period of taking study medication (See Appendix, section 20.2, page 95).
- 8. The participant is either unable to conceive/father children AND/OR his/her partner is unable to conceive/father children AND/OR they will consent to be using effective methods of contraception when engaging in heterosexual intercourse, as defined below:
  - a. Non-childbearing potential:
    - Female participant/sexual partner of male participant: Bilateral oophorectomy, and/or hysterectomy or bilateral tubal ligation more than 12 months ago and/or has been postmenopausal with a history of no menses for at least 12 consecutive months
    - ii. Male participant/sexual partner of female participant: Vasectomised or has had a bilateral orchidectomy minimally three months prior to screening
    - iii. Male participants having a pregnant female partner or a male sexual partner: At least one barrier method has to be used in this case.
  - b. Effective contraception methods:

- i. Female participants: Two methods, including methods that the patient's sexual partner(s) use. At least one must be a barrier method. Contraception must be practised for at least until 12 weeks after the last dose of DZD.
- Male participants: Two methods, including methods that the patient's female sexual partner(s) use. At least one must be a barrier method.
   Effective contraception must be ensured for at least 16 weeks after the last dose of DZD.

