5.5. Exploratory Endpoints

Exploratory endpoints will be analysed depending on laboratory capacity and budget and may not be tested in all trial's sites equally. Refer to DECODE Protocol for more details.

6. Analysis Populations

The ITT analysis population will be primary for all analyses, apart from safety analyses where the safety population will be primary. The Adequate adherence (AA) population will be secondary.

6.1. Intent-to treat (ITT) population:

The ITT population will consist of all randomized participants in the groups to which they were randomly assigned, and who have taken at least one dose of study treatment.

6.2. Modified Intent-to treat (MITT) population:

The MITT population will be the same with ITT population but exclude participants that withdrew from study medications prior to PK sampling.

6.3. Adequate adherence (AA) population:

The AA population will be the same as the ITT population with the following participants excluded:

· Randomized participants not meeting the eligibility criteria

• Participants having missed one or more doses on 10 or more days of their allocated treatment.

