Table 2.2 Summary of Culture Results by Randomized Treatment of Week 02.

{Similar shell table as Table 2.1}

Table 2.3 Summary of Culture Results by Randomized Treatment of Week 08.

{Similar shell table as Table 2.1}

Table 2.4 Summary of Culture Results by Randomized Treatment of Week 12.

{Similar shell table as Table 2.1}

Table 2.5 Summary of Culture Results by Randomized Treatment of Week 14.

{Similar shell table as Table 2.1}

Table 2.6 Summary of Culture Results by Randomized Treatment of Week 16.

{Similar shell table as Table 2.1}

Table 2.7 Summary of Time to Positivity (TTP) by Treatment Arm of Week 00*.

TTP	Arm 1 D0 (N=x) n (%)	Arm 2 D400 (N=x) n (%)	Arm 3 D800-OD (N=x) n (%)	Arm 4 D1200 (N=x) n (%)	Arm 5 D800-BD (N=x) n (%)	Total (N=x) n (%)
Mean (SD)	xx	xx	xx	xx	xx	xx
Median	xx	xx	xx	xx	xx	xx
Min – Max	(xx, xx)	(xx, xx)	(xx, xx)	(xx, xx)	(xx, xx)	(xx, xx)

^{*}Same tables will be applied to each week (from week 00 to week 16).

Table 2.8 Analysis of Time to Culture Conversion on Liquid Media.

TTP	Arm 1 D0 (N=x) n (%)	Arm 2 D400 (N=x) n (%)	Arm 3 D800-OD (N=x) n (%)	Arm 4 D1200 (N=x) n (%)	Arm 5 D800-BD (N=x) n (%)
25th centile, weeks	xx	xx	xx	xx	xx
Median (50th centile), weeks	xx	xx	xx	xx	xx
75th centile, weeks	xx	xx	xx	xx	xx
Mean	xx	xx	xx	xx	xx

v1.0, February 13, 2023

% With culture conversion at 0 week					
% With culture conversion at 2 weeks	xx.x%	xx.x%	xx.x%	xx.x%	xx.x%
% With culture conversion at 4 weeks	xx.x%	xx.x%	xx.x%	xx.x%	xx.x%
% With culture conversion at 6 weeks	xx.x%	xx.x%	xx.x%	xx.x%	xx.x%
% With culture conversion at 8 weeks	xx.x%	xx.x%	xx.x%	xx.x%	xx.x%
% With culture conversion at 12 weeks	xx.x%	xx.x%	xx.x%	xx.x%	xx.x%
% With culture conversion at 14 weeks	xx.x%	xx.x%	xx.x%	xx.x%	xx.x%
% With culture conversion at 16 weeks	xx.x%	xx.x%	xx.x%	xx.x%	xx.x%
Unadjusted Hazard Ratio (95% CI)	1	xx(xx, xx)	xx(xx, xx)	xx(xx, xx)	xx(xx, xx)
Adjusted Hazard Ratio (95% CI)*	1	xx(xx, xx)	xx(xx, xx)	xx(xx, xx)	xx(xx, xx)

^{*} Analysis has been adjusted for: gender, age, race, BMI, HIV status, baseline culture (using time to positivity)

Table 2.9 Analysis of Time to Culture Conversion on Solid Media.

TTP	Arm 1 D0 (N=x) n (%)	Arm 2 D400 (N=x) n (%)	Arm 3 D800-OD (N=x) n (%)	Arm 4 D1200 (N=x) n (%)	Arm 5 D800-BD (N=x) n (%)
25th centile	xx	xx	xx	xx	xx
Median (50th centile)	xx	xx	xx	xx	xx
75th centile	xx	xx	xx	xx	xx
% With culture conversion at 0 week	xx.x%	xx.x%	xx.x%	xx.x%	xx.x%

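### The liquid-culture conversion rule needs no earlier positive culture, so a participant with negative cultures from baseline is scored as converted at week 0

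*SAP*

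**What the plan says.** **Entry.** Protocol 10.3 asks for "presence of MTB complex and rapid molecular tests result confirming susceptibility to RIF and INH" and for "Sputum positive on microscopy from concentrated sputum for acid-fast bacilli on at least one sputum sample". No inclusion or exclusion criterion asks for a culture result.

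**Analysis sets.** SAP section 6 states: "The ITT analysis population will be primary for all analyses, apart from safety analyses where the safety population will be primary". ITT is "all randomized participants in the groups to which they were randomly assigned, and who have taken at least one dose of study treatment". MITT is ITT but will "exclude participants that withdrew from study medications prior to PK sampling". The AA set drops ineligible and poorly adherent participants, and the safety set needs one dose. None of the four uses a culture result.

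**Conversion.** SAP 11.4 requires "two consecutive culture negative timepoints without an intervening culture positive timepoint. Any other results will be ignored for the calculation of time to culture conversion". Time starts at randomisation, and positives after conversion do not undo it. Protocol 9.2.2 dates the event to the first negative culture and also sets no prior-positive condition. Two WK00 samples are cultured in MGIT (Protocol 11.2), and the negative-timepoint definition in SAP 11.1 is not limited to visits after baseline.

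**Uses of the rule.** SAP 12.1 gives Kaplan-Meier estimates by arm and a Cox comparison with the arm without delpazolid, adjusted for baseline TTP. Shell Table 2.8 shows unadjusted and adjusted hazard ratios together. SAP 12.5 does not replace missing data. SAP 11.2 uses conversion by week 8 to define who enters the relapse analysis.

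**The concern.** Conversion is meant to record a change from positive to negative on treatment. As written, the rule also credits participants who had nothing to convert from, and it gives them the earliest possible event time. With 15 per arm, one such participant is visible in the early Kaplan-Meier estimates and in the unadjusted hazard ratio.

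The same participant has no baseline TTP. With no imputation planned, he or she would probably drop out of the adjusted Cox model but remain in the unadjusted one. The two hazard ratios in Table 2.8 could then rest on different participants, and the SAP does not say how this is handled.

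The participant can also enter the relapse analysis without a baseline isolate to compare with a recurrence.

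**Working it through.** The SAP gives no figure for the conversion endpoint, so there is none to reproduce. The check has two parts.

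**1. Applying the rule to culture sequences, WK00 to WK16.** Contaminated and missing timepoints are ignored, as SAP 11.4 says. The event is dated at the first negative of the pair. The 28-day variant is read as two negatives at least 28 days apart with no positive between them. Entries are the week of conversion.

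| Pattern | SAP 11.4 main | 28-day variant | No later positive to week 16 | If a prior positive were required |
|---|---|---|---|---|
| Negative at every visit | 0 | 0 | 0 | no event |
| WK00 contaminated or missing, then negative | 1 | 1 | 1 | no event |
| Negative WK00–01, positive WK02–06, then negative | 0 | 7 | 7 | 7 |
| Negative WK00, positive WK01–06, then negative | 7 | 7 | 7 | 7 |
| Positive WK00–06, then negative | 7 | 7 | 7 | 7 |

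Week 0 is day 1 on the day count of SAP 12.6. If the event were dated at the second negative, the first row would read week 1. Rows 1 and 2 escape every planned definition. Row 3 is misdated only by the main definition. Row 4 is dated correctly, so a single negative WK00 does no harm.

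**2. Size in one arm.** The input is 15 per arm (SAP 4.3). Let p be the proportion converted among the other 14.

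- With the participant included: (14p + 1)/15.
- With the participant excluded: p.
- Difference: (14p + 1)/15 − p = (1 − p)/15.

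| p | Shift, percentage points |
|---|---|
| 0 (week 0) | 1/15 = 6.7 |
| 50% | 0.50/15 = 3.3 |
| 80% | 0.20/15 = 1.3 |
| 12/14 | 13/15 − 12/14 = 86.7 − 85.7 = 1.0 |
| 100% | 0 |

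**Illustration for the unadjusted hazard ratio.** This rests on assumptions that are not in the documents: 15 versus 15, median conversion about 7 weeks, weekly visits, censoring at week 16, no true effect, 1,500 simulated trials. One baseline-negative participant in the delpazolid arm multiplied the hazard ratio by about 1.09, and two by about 1.19, compared with leaving them out.

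**The case against.** Entrants are previously untreated, smear-positive and MTB-positive on a molecular test. Two samples are cultured at WK00, and one positive makes the timepoint positive. Affected participants should therefore be uncommon. They would fall across arms by chance, so including them adds noise and does not favour a dose. The adjusted Cox model would probably omit them, and shell Table 1.6 already shows baseline culture status by arm. All of this stands, and it limits the size of the problem. It does not make the week-0 event time meaningful.

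Stronger readings are tempting, but the documents do not support them:

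- **A shift of 6.7 points at every visit.** That is the week-0 value. Against exclusion the shift shrinks as the other participants convert.
- **Near-certainty that such a participant occurs.** Assumed rates of 1% and 5% without a positive baseline culture would give 1 − 0.99^75 = 53% and 1 − 0.95^75 = 98% for at least one in 75. The documents give no such rate, and the group includes participants who grow MTB at the next visits and are dated correctly.
- **The table shells show that the authors intended this.** Table 2.8 has a row "With culture conversion at 0 week", but its cells are blank in the text available. The row with placeholders is in Table 2.9, on solid media. The baseline rows of Table 1.6 repeat the generic result codes of SAP 11.1.
- **The relapse default is an error.** SAP 11.2 says: "If strain typing results are missing or inconclusive, a recurrence will be considered a relapse (rather than a reinfection". This is an explicit, conservative choice, and the protocol's relapse denominator does not depend on a baseline isolate.

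**Conclusion.** The point holds for the liquid-culture conversion endpoints. A stated rule gives a wrong event time, week 0 or week 1, to participants whose cultures are negative from the start, and for those negative throughout neither sensitivity definition corrects it. The effect per participant is (1 − p)/15 in an arm of 15, so it matters early and almost vanishes late. How many participants are affected is unknown. That the adjusted model would drop them is an inference from the missing-data rule, not something the SAP states.

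These are secondary endpoints. The primary exposure-response analysis of TTP does not use the conversion rule, and no bias towards any arm is shown. The change should be made because it is cheap and because it puts the Kaplan-Meier estimates and both hazard ratios on nearly the same participants.

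**What to change.** In SAP section 6 and 11.4:

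- Base the main time-to-conversion and proportion-converted analyses on ITT participants with at least one MGIT culture positive for MTB complex, with or without contamination, from WK00 or any other pre-treatment sample actually cultured. MGIT is scheduled only from WK00. Protocol 13.2 and SAP 12.1 suggest that screening samples may be cultured, but Protocol 10.5.1 lists no such test, so the flag should not depend on one.
- Do not let WK00 serve as the first negative of a conversion pair.
- State how a contaminated or missing WK00 is handled. One option is a sensitivity analysis that adds participants who later grow MTB, dating conversion only after their first positive. Later growth is observed after randomisation, so it should not define the main set.
- Report the number excluded per arm and keep full ITT as a sensitivity analysis.
- Keep the protocol's relapse denominator, and flag and report separately anyone in it without a baseline isolate.

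The cost is some SAP wording and one derived variable. A few participants leave the main conversion analyses, on a characteristic fixed before treatment, so the randomised comparison is not biased. The safety and PK sets do not change.
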